1. Confirmed PD: The assessment of PD by RECIST v1.1 (baseline PD assessment) will be confirmed by a repeat evaluation at the next tumor assessment time point, but no sooner than 4 weeks later. If any subsequent tumor assessment time point shows $\geq 20\%$ increase in the overall tumor burden (the sum of diameters of target lesions and new lesions), when compared to the baseline PD assessment (the sum of diameters of target lesions and new lesions), the subject would be deemed as having confirmed PD.
 - a. Note: Subjects in Arm B (MEDI4736 monotherapy) and Arm C (tremelimumab monotherapy) of Phase 2 who experience a confirmed PD (as defined above) will have the option (on a case-by-case basis) to crossover to treatment with MEDI4736 in combination with tremelimumab (using the Phase 2 schedule) for 12 months or until a second confirmed PD. Crossover will be permitted as long as the treatment beyond progression criteria are met and any of the investigational product discontinuation criteria (with the exception of criterion number 10 in Section 4.1.6) are not met. If crossover is not chosen by the investigator, then the study treatment must be discontinued.
 - b. Note: Subjects with confirmed PD during 12 months of treatment with MEDI4736 in combination with tremelimumab (Phase 1b, and Arms A and D, and E of Phase 2) may not crossover to either MEDI4736 monotherapy or tremelimumab monotherapy at any time. Subjects enrolled in Phase 1b, and Arms A, D, and E of Phase 2 who exhibit confirmed PD after completing the planned 4 doses of combination treatment, but prior to completing the 12-month dosing period (ie, while receiving MEDI4736 monotherapy) may be eligible for reinduction (on a case-by-case basis) with combination therapy and continued treatment for an additional 12 months (or until the subject meets any of the discontinuation criteria listed below). The subject would be readministered investigational products according to the same treatment guidelines followed during their initial treatment. Subjects who are enrolled in Phase 1b and Arms A, D, and E of Phase 2 and who exhibit disease progression prior to completing the planned 4 doses of combination treatment may be eligible for continued treatment through the end of the planned 12-month treatment period (or until the subject meets any of the discontinuation criteria listed below), but will not be eligible for reinduction.

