3.4.1 Primary Efficacy Endpoints and Analyses

Arms A, B, C and E

The two co-primary efficacy endpoints are Objective response (OR) and PFS-6 based on RECIST v1.1.

Arm D

The primary efficacy endpoint is objective response (OR) based on RECIST v1.1.

The primary efficacy analyses for the primary efficacy endpoint(s) will be based on the As-treated Population.

Objective Response

Objective response (OR) is defined as best overall response (BOR) of confirmed CR or confirmed PR according to RECIST v1.1. The best overall response is defined as the best response (in the order of CR, PR, SD, PD, and not evaluable) among all overall responses recorded from the date of randomization for Phase 2 Arm A, B and C subjects or the date of first dose of study treatment for Phase 1b and Phase 2 Arm D and E subjects until progression, or the last evaluable disease assessment in the absence of PD prior to the initiation of subsequent anticancer therapy or discontinuation from the study, whichever occurs first.

The best overall response (BOR) of CR or PR must be confirmed, which means a response of CR/PR is recorded at 1 visit and confirmed by repeat imaging not less than 28 days (4 weeks) after the visit when the response was first observed with no evidence of progression between the initial and CR/PR confirmation visit. A confirmed CR is defined as two CRs that were

separated by at least 28 days with no evidence of progression in-between. A confirmed PR is defined as two PRs or an un-confirmed PR and an un-confirmed CR that were separated by at least 28 days with no evidence of progression in-between. For a subject to qualify for a BOR of SD, at least 54 days from the randomization date or start of treatment date must elapse without disease progression. The definition of 54 days reflects the protocol-defined disease assessment window of ± 3 days (Day 57 plus/minus 3 days).

Subjects who responded with an unconfirmed CR/PR at the time of data cutoff will be reported as CR/PR pending confirmation under the SD category provided the minimum criteria for SD duration (54 days) are met, otherwise this will be reported under the Non Evaluable (NE) category. NE is assigned for a subject who has only a baseline assessment, or a response assessment of CR/PR/SD at an interval of less than 54 days since randomization or the start of treatment and who has no subsequent disease evaluation, or has all overall response evaluations assessed as NE.

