- DSD is defined as the time from the date of randomization for Phase 2 Arm A, B, and C subjects or the date of first dose of study treatment for Phase 1b and Phase 2 Arm D and Arm E subjects until the first date of documented PD (per RECIST v1.1), or death due to any cause, whichever occurs first. DSD will be analyzed for subjects with SD as their BOR per RECIST v1.1. The median DSD with 90% and 95% CI will be estimated based on the Kaplan-Meier curves. For subjects who are alive and progression-free at the time of data cut-off, DSD will be censored at the PFS censoring time.
- Best percentage change from baseline of the SLD of target lesions per RECIST v1.1 will be derived as the biggest decrease or the smallest increase from baseline on the SLD among all post-baseline disease assessment including unscheduled assessments. Best percentage change from baseline in the SLD of target lesions by subject will be presented in a 'Waterfall' plot, to show each subject's best percentage as a separate bar, with the bars ordered from the largest increase to the largest decrease. Additionally, the percent change from baseline in the SLD of target lesion at each post-baseline disease assessment will be summarized by treatment group with descriptive statistics.
- PFS is defined as in section 3.4.1.2. PFS-9 is the 9-month PFS rate, which is the proportion of subjects who are progression free and alive at 9 months. Similar to PFS-6, Kaplan-Meier curves will be generated for PFS and used to estimate median PFS and the PFS-9 rate along with their 2-sided 90% and 95% CIs.
- Overall survival is defined as the time from date of randomization for Phase 2 Arm A, B, and C subjects or the date of first dose of study treatment for Phase 2 Arm D and Arm E

subjects until death due to any cause. If there is no death reported for a subject by the data cut-off date, OS will be censored at last known alive date. If the last known alive date is after the data cutoff date, OS will be censored at the date of data cutoff for that subject. Kaplan-Meier curves will be generated for OS and used to estimate the median OS and the 1-year survival rate along with their 2-sided 90% and 95% CIs.

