3.4.4 Other Efficacy Analyses

In addition, sensitivity analyses for response-related endpoints and corresponding time-to-event endpoints for primary and secondary efficacy endpoints will be based on overall response reported based on investigator assessment if there is sufficient discrepancy.

Sensitivity analyses for ORR, DCR-16w and DCR-24w will be performed based on the Response Evaluable Population.

Sensitivity analyses for the ORR, DCR-16w, DCR-24w, DoR, PFS, PFS-6, and PFS-9, all derived according to RECIST v1.1 modified for confirmation of PD may be performed. Under RECIST v1.1 with modification, any objective disease progression must be confirmed by the next scheduled scan. The confirmatory scan must be no sooner than 4 weeks after the initial suspected progression. If disease progression is confirmed (or disease progression occurs and no further scans are recorded) then the date of progression will be when it was originally observed. Subjects with a single disease progression and no further tumor assessment scans will be treated as PD in the analysis. For such sensitive analysis, tumor data obtained up until confirmed progression, or the last evaluable assessment in the absence of a confirmed progression (prior to starting new anticancer therapy), will be included in the

assessment of BOR, ORR and DCR. Note that the response or disease control may occur after an unconfirmed progression.

[REDACTED]

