3.8 Safety Analyses

In Phase 1b, the number of DLTs that are identified in the DLT Evaluable Population during the DLT evaluation period will be summarized and listed. Safety data including AEs, SAEs, laboratory parameters, ECGs, vital signs and ECOG performance status, will be summarized in the As-treated population by treatment group, pooled dose groups and overall.

Repeated or unscheduled tests will not be summarized for each scheduled visit, but will be included for summaries of “worst-case” on treatment values and shift-table analyses. “Worst-case” on treatment (i.e. maximum or minimum on-treatment value depending on the direction of an adverse effect) is defined as the nadir and/or zenith including any scheduled and unscheduled post-baseline assessments that occur through the last assessment on-treatment. The last assessment on-treatment is defined as the last visit with a non-missing observation that occurred up till 90 days (+7 days to allow for a visit window) following the last dose of study treatment (if safety follow-ups are performed till 90 days after the last dose), or till the initiation of the subsequent anticancer therapy (excluding palliative radiotherapy), whichever occur first.

If the number of subjects with available data is less than 10% of the total number of subjects in the As-treated Population for overall summary for the dose escalation phase, or for each cohort in the dose expansion phase at a scheduled time of evaluation, no summary statistics will be presented at that time point, unless otherwise indicated.

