3.8.1 Adverse Events and Serious Adverse Events

Adverse events will be coded using Medical Dictionary for Regulatory Activities and assigned grades based on NCI CTCAE v4.03.

Treatment-emergent adverse event (TEAE) will be defined for the initial treatment period and subsequent treatment periods separately. TEAEs are defined as any adverse events that occur on or after the date of initial receipt of study treatment during each treatment period. Analysis of AEs (as described below) will be limited to TEAEs. Any AEs that are considered as non-treatment emergent will be presented in the listings only.

For both Phase 1b and Phase 2, the number and percentage of subjects reporting treatment-emergent AEs will be summarized overall and by the worst NCI CTCAE v4.03 grade, system organ class, and preferred term. Similarly, the number and percentage of subjects reporting treatment-emergent AEs considered related to investigational product will be summarized. At each level of subject summarization, a subject will be counted once using the highest grade and level of causality if one or more occurrences of the same system organ class/preferred term is reported. SAE will be summarized overall, by system organ class and preferred term, and by SAE criteria. The number and percentage of subjects reporting treatment-emergent SAEs considered related to investigational product will also be summarized.

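### Best percentage change in target lesions and the on-treatment safety extremes have no stated cut at crossover, so combination-phase data can be counted in monotherapy Arms B and C

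*SAP*

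**What the plan says.** SAP 3.4.2 lists best percentage change in SLD as a secondary endpoint for both phases. It is the largest decrease or smallest increase "among all post-baseline disease assessment including unscheduled assessments", shown as one bar per subject in a waterfall plot. Percent change at each assessment is also summarised by treatment group. SAP 3.1 sets baseline before the first dose of study drug and gives no new baseline for later periods.

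SAP 3.8 defines worst-case safety values as extremes "including any scheduled and unscheduled post-baseline assessments that occur through the last assessment on-treatment". That last assessment may fall up to 90 (+7) days "following the last dose of study treatment (if safety follow-ups are performed till 90 days after the last dose", or at the start of subsequent anticancer therapy if earlier. SAP 3.8.4, 3.8.5.1 and 3.8.5.3 apply on-treatment windows to laboratory values, vital signs and ECOG status. SAP 3.8.5.2 takes notable ECG values over all post-baseline evaluations.

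Under Protocol 3.1.2.4, Arm B and C subjects with confirmed PD "will have the option (on a case-by-case basis) to crossover to treatment with MEDI4736 in combination with tremelimumab", for up to 12 months or until a second confirmed PD. Protocol 4.2.2 reuses the same visit schedule after crossover.

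**The concern.** Nearby rules in the same SAP do stop or split. Best overall response runs "until progression, or the last evaluable disease assessment in the absence of PD prior to the initiation of subsequent anticancer therapy". Treatment-emergent adverse events "will be defined for the initial treatment period and subsequent treatment periods separately". The SLD rule and the safety-extreme rules do neither at crossover.

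A best or worst value over a window can only become more extreme as the window lengthens. If crossover data are included, the waterfall for Arms B and C can only look better, which flatters monotherapy against Arm A. The worst-case laboratory, vital-sign and ECG values can only look worse, which makes monotherapy appear more toxic. Last on-treatment values would describe the combination, in either direction. These displays would sit beside the formal A-versus-B and A-versus-C comparisons of ORR and PFS-6, and the waterfall could disagree with ORR for a reason the reader cannot see.

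**Working it through.** The plan states no figure to reproduce, so the check compares data windows and then sizes the effect under stated assumptions.

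**1. Windows side by side**

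| Quantity | Where data stop | Excludes crossover data? |
|---|---|---|
| Best overall response (SAP 3.4.1) | Progression, or before other anticancer therapy | Yes, since crossover needs confirmed PD |
| Confirmed-PD sensitivity analysis (SAP 3.4.4) | Uses "tumor data obtained up until confirmed progression" | Yes, since crossover follows that point |
| Treatment-emergent AEs (SAP 3.8.1) | Split by treatment period | Yes |
| Best percentage change in SLD (SAP 3.4.2) | No stop given | No |
| Worst-case and last on-treatment values (SAP 3.8) | 90 (+7) days after last study dose, or other anticancer therapy | Not stated |
| Notable ECG values (SAP 3.8.5.2) | No stop given | No |

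**2. Which later courses change the regimen (Protocol 3.1.2.4)**

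- Crossover: Arms B and C move from monotherapy to the combination.
- Reinduction: only Phase 1b and Arms A, D and E, which already receive the combination. The missing cut mixes two courses of one regimen.
- Retreatment: the regimen given at study entry, so again two courses of one regimen. However, the Re-treated Population in SAP Table 3.2-1 and Protocol 4.8.1 is limited to subjects re-treated with the combination. The two wordings conflict for Arms B and C.

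**3. When a crossover subject's bar changes**

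Reported best change = min(best before crossover, best after crossover), both relative to the original baseline. It changes only if a post-crossover SLD falls below the subject's earlier best. Illustration, assuming growth in target lesions only and nadir equal to baseline:

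- SLD at first PD: 1.20 × baseline.
- SLD at confirmed PD, a further 20%: 1.20 × 1.20 = 1.44 × baseline.
- After a 30% fall on the combination: 1.44 × 0.70 = 1.01 × baseline, a change of about zero.
- Fall needed to reach −30% from baseline: 1 − 0.70/1.44 = 51%.

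Subjects who progress through new or non-target lesions could need a smaller fall.

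**4. Effect on the share at −30% or better**

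Rise = c × r, where c is the share crossing over and r the share of those who first reach −30% from original baseline afterwards. Both are assumed.

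- Low: 0.10 × 0.05 = 0.5 percentage points.
- High: 0.40 × 0.20 = 8 percentage points.

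Arm sizes are also assumed. Protocol 3.1.1 gives 89 enrolled in Arms A to D; less the 25 planned for Arm D (SAP 2.4.2), 64 remain, or about 26, 26 and 13 at 2:2:1. In subjects, the range is 0.1 (26 × 0.005) to 2.1 (26 × 0.08) in Arm B, and 0.1 (13 × 0.005) to 1.0 (13 × 0.08) in Arm C.

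**5. Longest safety window in Arms B and C, without retreatment**

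97 days ÷ 30.44 days per month = 3.2 months.

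- Initial period only: 12 + 3.2 = 15.2 months.
- With crossover at month 12: 12 + 12 + 3.2 = 27.2 months.
- With crossover at month 4: 4 + 12 + 3.2 = 19.2 months.

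**The case against.** The strongest reply is that the SAP already separates the phases. As-treated subjects are analysed by the treatment they actually receive, Crossover and Re-treated populations are defined, disposition is split by initial treatment and re-treatment, and details are left to a statistical programming plan that is not among the documents. It follows that misattribution is possible, not demonstrated. But the As-treated wording does not say how two sequential regimens in one subject are handled, and a separate crossover analysis does not remove those data from the main one. Protocol 4.8.1 makes the separate analyses optional, and SAP 3.2 lets them be reduced when numbers are small.

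Crossover might also be read as subsequent anticancer therapy. Protocol 3.1.2.4 exempts crossover from discontinuation criterion 10 in Protocol 4.1.6, the one about starting other anticancer therapy, which leaves room for that reading. It would close the SAP 3.8 window at crossover, but not the SLD or ECG rules, which have no such limit.

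Three stronger conclusions are tempting, and the documents do not support them:

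- That reinduction and retreatment also put combination data into the monotherapy arms. Protocol 3.1.2.4 rules this out; only the Re-treated definition suggests otherwise.
- That each crossover subject whose tumour shrinks by 30% adds a full subject to the apparent shrinkers (1/26 = 3.8 points in Arm B, 1/13 = 7.7 in Arm C). Change is measured from the original baseline, after growth to confirmed PD, so this holds only for a subject who newly passes −30% from that baseline.
- That scans under later non-study therapy are a major route. Protocol 4.2.3 no longer requires follow-up visits once alternative treatment starts.

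**Conclusion.** The gap is real and limited. Taken literally, the SLD rule and the ECG rule include combination-phase data from Arm B and C crossover subjects. The worst-case and last on-treatment rules do so unless crossover is treated as subsequent anticancer therapy, which the SAP does not say.

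Confirmed ORR and PFS-6 are unaffected, because best overall response stops at progression and PFS takes the first progression. Best percentage change carries no planned test. A reader might infer that the primary comparisons are biased; they are not.

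The size cannot be established from the documents. The 0.5 to 8 point range rests wholly on the assumed crossover and response shares, and the 27-month window is the longest case, not a typical one. The change is worth making because the direction is known for best and worst values and the cost is small.

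**What to change.** - For the initial treatment period, limit best percentage change, percent change by visit, and worst-case and last on-treatment laboratory, vital-sign, ECG and ECOG values to data before the first dose of crossover, and likewise of reinduction or retreatment. For SLD, also stop before any subsequent anticancer therapy.
- Do not cut at first RECIST v1.1 PD. Protocol 4.3.1.1 deliberately keeps subjects on their assigned regimen beyond that point to capture late responses, and those scans are not contaminated by crossover.
- Report later periods separately with a stated baseline for each, following the split by period in SAP 3.8.1.
- Reconcile the Re-treated Population definition (SAP Table 3.2-1, Protocol 4.8.1) with the same-regimen wording in Protocol 3.1.2.4.

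The cost is a few SAP sentences, a date filter in programming, and moving some late shrinkage from the main waterfall to a separate display.

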3.4.3 Subgroup Analyses

In order to assess the consistency of treatment effect, the efficacy analyses of ORR, DCR-16w, DCR-24w, DoR, PFS, and PFS-6 will be summarized based on the As-treated population for the following subgroups provided sufficient data are available:

- PD-L1 status (positive, negative, unselected)
- Age (<65, ≥ 65 yrs.)
- Region (US, rest of world)
- Race (Asian, non-Asian)

3.4.4 Other Efficacy Analyses

In addition, sensitivity analyses for response-related endpoints and corresponding time-to-event endpoints for primary and secondary efficacy endpoints will be based on overall response reported based on investigator assessment if there is sufficient discrepancy.

Sensitivity analyses for ORR, DCR-16w and DCR-24w will be performed based on the Response Evaluable Population.

Sensitivity analyses for the ORR, DCR-16w, DCR-24w, DoR, PFS, PFS-6, and PFS-9, all derived according to RECIST v1.1 modified for confirmation of PD may be performed. Under RECIST v1.1 with modification, any objective disease progression must be confirmed by the next scheduled scan. The confirmatory scan must be no sooner than 4 weeks after the initial suspected progression. If disease progression is confirmed (or disease progression occurs and no further scans are recorded) then the date of progression will be when it was originally observed. Subjects with a single disease progression and no further tumor assessment scans will be treated as PD in the analysis. For such sensitive analysis, tumor data obtained up until confirmed progression, or the last evaluable assessment in the absence of a confirmed progression (prior to starting new anticancer therapy), will be included in the

assessment of BOR, ORR and DCR. Note that the response or disease control may occur after an unconfirmed progression.

[REDACTED]

3.4.5 Handling of Dropouts and Missing Data

Missing target lesion measurement data

For the disease response derivation in target lesion (TL) data, if a lesion size is missing due to the lesion being too small to be measured, the missing value is defaulted to 5 mm. If a lesion size is missing due to technical difficulty of the measurement (i.e., poor quality of scan, blurring lesion etc.), the measurement for that lesion will not be imputed and the target lesion visit response is not evaluable (NE). Overall visit response will also be NE. However, a visit response of PD should still be assigned if any of the following occurred:

- A new lesion is recorded
- A non-target lesion (NTL) visit response of PD is recorded
- The sum of TLs is sufficiently increased to result in a 20% or greater increase, and an absolute increase of ≥ 5 mm, both from nadir even assuming the non-recorded TLs have disappeared

3.5 Patient Reported Outcomes

3.5.1 EORTC QLQ-C30 and Analysis of EORTC QLQ-C30

The EORTC QLQ-C30 v3.0 is a 30-item self-administered questionnaire. EORTC QLQ-C30 is measured at baseline, during treatment and during the follow-up period. The scoring of the symptom scales/items will follow the EORTC scoring manual. Individual items will be assessed using untransformed scores but for each of the 15 domains (9 multiple-item scales, 6 single-item scales), final scores are transformed such that they range from 0-100; higher scores indicate greater functioning, greater quality of life, or greater level of symptom burden ([Aronson et al, 1993](#)).

For each subscale, if less than 50% of the subscale items are missing, then the subscale score will be divided by the number of non-missing items and multiplied by the total number of items on the subscales. If at least 50% of the items are missing, then that subscale will be treated as missing. Missing single items are treated as missing. The reason for any missing questionnaire will be identified and recorded. If there is evidence that the missing data are systematic, missing values will be handled to ensure that any possible bias is minimized.

Table 3.5.1-1 Time to deterioration of Health Related QoL

Score	Change from baseline	Visit response
EORTC QLQ-C30 multiple-item scales: Global HRQoL score; functional scale (physical, role, emotional, cognitive, and social) scores; symptom scale (fatigue, pain, nausea & vomiting) scores	Increase of 10 points or more	Improved
	Decrease of 10 points or more	Deterioration
	Otherwise	No change
EORTC QLQ-STO22 Symptom scores: STODYS (dysphagia) score, STOEAT (eating restrictions) score, STOPAIN (stomach pain) score, STOFX (reflux) score,	Decrease of 10 points or more	Improved
	Increase of 10 points or more	Deterioration
	Otherwise	No change

The deterioration must be sustained for at least 21 days (i.e. there must be no response of “improved” or “no change” within 21 days of the visit response of “deterioration”).

Higher scores on the functional scales indicate a higher level of functioning and on the global HRQoL score indicate a better quality of life. Higher scores on the symptom scales/items indicate a higher symptom burden.

Time to deterioration of will be calculated for the multiple-item scales: 5 functional scales (physical, role, emotional, cognitive and social); 3 multi-item symptom scales (fatigue, pain, nausea and vomiting) and a 2-item global HRQoL scale. A change of at least 10 points in the score will be considered as a clinically relevant or a minimally important difference (Table 3.5.1-1).

Time to deterioration of a multiple-item scale will be defined as the time from date of randomization for Phase 2 Arm A, B, and C subjects or the date of first dose of study treatment for Phase 1b and Phase 2 Arm D and Arm E subjects to the date of a clinically important deterioration or death (by any cause) in the absence of a clinically meaningful deterioration regardless of whether the patient withdraws from treatment or receives another anti-cancer therapy prior to deterioration in the multiple-item scale score. Death will be included as an event only if the death occurs within two visits of the last PRO assessment

where the symptom change could be evaluated.

Subjects whose multiple-item scale score has not shown a clinically meaningful deterioration and who are alive at the time of the analysis will be censored at the time of their last EORTC assessment where the symptom could be evaluated. Also, if the multiple-item scale score deteriorates after 2 or more missed EORTC assessment visits or the patient dies after 2 or more missed EORTC assessment visits, the patient will be censored at the time of the last EORTC assessment where the multiple-item scale score could be evaluated. Time to deterioration of the multiple-item scales will be analyzed using the same methodology and model as described for the analysis of PFS.

Summary tables of the absolute change from baseline for domains and subscale scores will be summarized descriptively.

Compliance overall and over time will be summarized by treatment groups for the EORTC QLQ-C30 questionnaire. These will be based upon:

- Received forms = number of EORTC QLQ-C30 forms received back.
- Expected forms = number of subjects still under QoL follow-up at the specified assessment time excluding subjects in countries with no available translation. For subjects whose disease has progressed, the latest of progression and safety follow-up will be used to assess whether the patient was under QoL follow-up at the specified assessment time. Date of study discontinuation will be mapped to the nearest visit date to define the number of expected forms. Evaluable forms = subset of expected EORTC QLQ-C30 forms with at least one subscale that can be determined

Overall compliance will be defined as the number of subjects who provided both a baseline and at least one post baseline assessment for which there were sufficient data recorded for the visit to be evaluable for at least one multi-item or single-item scale score, divided by the number of subjects treated/randomized. Compliance over time is calculated separately for each visit, including at baseline, as the number of subjects with an evaluable form at the time point (as defined above), divided by number of subjects expected to have completed forms at that visit. Similarly the evaluability rate over time will be calculated separately for each visit, including baseline, as the number of evaluable forms (per definition above), divided by the number of received forms.

Best QoL response per subject overall is defined as shown in Table 3.5.1-2 below.

Table 3.5.1-2 Best QoL response

Overall score response	Criteria
Improved	Two visit responses of “improved” a minimum of 21 days apart without an intervening visit response of “deterioration”
No change	Does not qualify for overall score response of “improved”. Two visit responses of either “no change” or “improved” and “no change” a minimum of 21 days apart without an intervening visit response of “deterioration”
Deterioration	Does not qualify for overall score response of “improved”. A visit response of “deterioration” without a response of “improved” or “no change” within 21 days
Other	Does not qualify for one of the above

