3.5.2 EORTC QLQ-STO22 and Analysis of EORTC QLQ-STO22

The EORTC QLQ-STO22, a disease-specific 22-item self-administered questionnaire for gastric cancer ([Vickery et al, 2001](#)), was developed to be used in conjunction with the EORTC QLQ-C30 v3.0. The scoring of the symptom scales/items will follow the EORTC scoring algorithm. For the symptom scales and items a higher score is equivalent to worse or more symptoms. In the functional scales, a high score is equivalent to better function.

Time to deterioration analysis will be conducted in the same for the following symptom scales of the EORTC QLQ-STO22 as described for the EORTC QLQ-C30 multiple-item scales: STODYS (dysphagia) score, STOEAT (eating restriction) score, STOPAIN (stomach pain) score, and STOFX (reflux) score. A change of at least 10 points in the score will be considered as a clinically relevant or a minimally important difference.

Change from baseline for each of the summary scales and single item measures described above will be summarized descriptively. Summary symptom scores: STODYS (dysphagia) score, STOEAT (eating restriction) score, STOPAIN (stomach pain) score, and STOFX (reflux) score will be included. Multiple item system scale STOANX (anxiety) and single item measures: STODM (dry mouth) score, STOT (taste) score, STOBI (body image) score, and STOHL (hair loss) score will not be summarized but will be presented in by-subject listings.

Similarly, compliance overall and over time will be summarized by randomized or assigned treatment for the EORTC QLQ-STO-22 questionnaire as was described for the EORTC QLQ-C30.

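### SAP Table 3.5.1-1 classifies change on the QLQ-C30 fatigue, pain and nausea/vomiting scales in the wrong direction: worsening counts as improvement and relief as deterioration

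*SAP*

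**What the plan says.** SAP Section 3.5.1 classifies each QoL visit by its change from baseline, using Table 3.5.1-1. The table has two rows.

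- **QLQ-C30 multiple-item scales.** This row holds global HRQoL, the five functional scales and "symptom scale (fatigue, pain, nausea & vomiting) scores". For all of them, "Increase of 10 points or more" is labelled Improved and "Decrease of 10 points or more" is labelled Deterioration.
- **STO22 symptoms.** The second row covers "EORTC QLQ-STO22 Symptom scores: STODYS (dysphagia) score, STOEAT (eating restrictions) score, STOPAIN (stomach pain) score, STOFX (reflux) score" and reverses the labels: a fall of 10 or more is Improved and a rise of 10 or more is Deterioration.

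The orientation of the scores is stated before the table ("higher scores indicate greater functioning, greater quality of life, or greater level of symptom burden") and again after it ("Higher scores on the symptom scales/items indicate a higher symptom burden"). Section 3.5.2 gives the same orientation for the STO22: "For the symptom scales and items a higher score is equivalent to worse or more symptoms".

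Two analyses use the visit labels. Time to deterioration is planned for the functional scales and for "3 multi-item symptom scales (fatigue, pain, nausea and vomiting) and a 2-item global HRQoL scale". Best QoL response in Table 3.5.1-2 is built from the same labels.

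**The concern.** A single direction rule cannot serve both functional and symptom scales when one set improves upward and the other downward. The rule in the QLQ-C30 row is right for global HRQoL and function, and backwards for fatigue, pain and nausea/vomiting.

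At stake are the patient-reported symptom results. A patient whose fatigue rises and stays up would have no deterioration event on that scale and could be reported as improved. A patient whose pain eases would be counted as having deteriorated. Depending on the balance of rises and falls, deaths and censoring, a comparison of arms on these three scales could point the wrong way. The report would also apply opposite rules to QLQ-C30 pain and STO22 stomach pain. A programmer following the SAP literally would produce the error, and a validator checking against the SAP would pass it.

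**Working it through.** The SAP gives no numerical result to reproduce here. The check applies its rule to changes in each direction and compares the label with the orientation it states.

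**Scales affected.** The multiple-item scales are 5 functional + 3 symptom + 1 global = 9. The row's rule is right for 5 + 1 = 6 and wrong for 3. The four STO22 symptom scores in the second row are right.

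**Visit labels (illustrative scores)**

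| Scale | Change | Meaning under the SAP's orientation | Label from Table 3.5.1-1 |
|---|---|---|---|
| QLQ-C30 physical function | 30 to 50 (+20) | better | Improved (correct) |
| QLQ-C30 fatigue | 30 to 50 (+20) | worse | Improved (wrong) |
| QLQ-C30 fatigue | 50 to 30 (−20) | better | Deterioration (wrong) |
| STO22 stomach pain | 30 to 50 (+20) | worse | Deterioration (correct) |

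Changes of less than 10 points are No change under either direction.

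**Effect at one visit.** Let u be the share of patients whose symptom score rises by 10 or more, and d the share whose score falls by 10 or more. The correct percentages are d improved and u deteriorated; the table reports u improved and d deteriorated. Correct net improvement is d − u and reported net improvement is u − d, an error of 2(u − d). The documents give neither share, so these are assumed values:

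| u | d | Correct net | Reported net | Error |
|---|---|---|---|---|
| 40% | 20% | −20 points | +20 points | +40 points |
| 30% | 30% | 0 | 0 | 0 |
| 20% | 40% | +20 points | −20 points | −40 points |

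Even in the middle case the net is right only because equal numbers of patients carry the wrong label in each direction.

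**Effect on the two derived outputs for fatigue**

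- *Two visits at +20, at least 21 days apart, nothing in between.* Correctly, this is a sustained deterioration: an event for time to deterioration and a best QoL response of Deterioration. As written, both visits are Improved, so there is no deterioration event from them and the best response is Improved.
- *A single visit at +20 with no other assessment.* Correctly, the best response is Deterioration. As written, the one Improved visit falls short of the two that Table 3.5.1-2 requires for Improved or for No change, so the best response is Other.

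The second case shows that the summary outputs are wrong without being exact mirror images of the truth.

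**Does other text correct the direction?** Section 3.5.1 gives the 10-point threshold without a direction and refers back to Table 3.5.1-1. Its reference to the EORTC scoring manual governs how the 0–100 score is computed, not how change is labelled. Table 3.5.1-2 contains no direction of its own. The SAP amendment table records QoL edits in versions 2.1 and 3.0, and the row still stands in the current text.

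**The case against.** The best case against this point concerns its reach.

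- QoL is not among the primary or secondary endpoints that can be read in the protocol. Parts of the objective and endpoint lists are redacted, so its formal rank cannot be confirmed. ORR, PFS-6 and the safety analyses are untouched. This stands.
- The derived outputs are not fully reversed. Time to deterioration also counts death within two visits of the last PRO assessment, and those events keep their meaning. Deterioration must be sustained for 21 days, and the categories of best QoL response have unequal requirements. This stands, so the percentage swap above applies to single-visit labels only.
- A visible conflict with the STO22 results is not inevitable. Pain is the only overlapping concept, and the STO22 scale measures stomach pain specifically. This stands too: the inconsistency shown is between rules, not necessarily between results.
- Descriptive summaries of change from baseline do not use the table and would be correctly oriented, so an alert reader might notice. That helps detection but does not make the classified outputs correct.

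One could also suspect a table broken in conversion from PDF. That is unlikely: the symptom scales follow a semicolon inside the QLQ-C30 cell, and there are exactly two sets of change rules, one per questionnaire.

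None of this supplies a reading under which the row is right for the symptom scales.

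**Conclusion.** The concern holds. The row contradicts the SAP's own statement of what a high symptom score means, and the rule the same table applies to STO22 symptoms. Every visit-level Improved or Deterioration call is inverted for 3 of the 9 multiple-item QLQ-C30 scales: fatigue, pain and nausea/vomiting. Time to deterioration and best QoL response for those scales inherit the error, though not as exact mirror images.

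The conclusion rests only on SAP text and assumes the table is programmed as written. The size of the distortion in any summary cannot be stated without the shares of patients rising and falling by 10 or more, which the documents do not give. It does not threaten the trial's main efficacy conclusions, but it must be corrected before these symptom results are reported, because followed literally the plan gives wrong answers.

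**What to change.** Split the first row of Table 3.5.1-1.

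- Global HRQoL and the five functional scales keep the present rule: +10 or more is Improved, −10 or less is Deterioration.
- QLQ-C30 fatigue, pain and nausea/vomiting take the STO22 rule: −10 or less is Improved, +10 or more is Deterioration.

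Table 3.5.1-2 needs no rewording, since it will inherit the corrected visit labels. Check the programs for visit response, time to deterioration and best QoL response against the corrected table, and rerun any affected output already produced.

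The cost is a short SAP correction and a program check. No new data are needed.
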